13.0 CRITERIA FOR REMOVAL FROM STUDY

Subjects participating may withdraw from the study at any time and for any reason.

Subjects may be removed from the study at any time due to severe unacceptable side effects, life-threatening events, (as described in Section 11), patient's non-compliance with the defined treatment plan, the patient becomes pregnant or the patient's request to withdraw consent.

For all participants, failure to have the planned surgery at MSKCC will result in removal from the study.

Patients will be replaced if they withdraw from the study after signing consent but prior to completing all study assessments.

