4.2 Intervention

During study intervention planning, the standard of care for patients with early stage primary breast cancer diagnosis and treatment of as well as the timing of the definitive surgery schedule will not be altered in any way for patients participating in this study. If a patient experiences side effects from intervention resulting in a delay of their planned surgery date, this will be a failure of the primary endpoint. The planned intervention of this study is to obtain image guided biopsies, percutaneous MRI or US guided breast tumor cryoablation, and ipilimumab/nivolumab administration.

Most patients will have an outside biopsy confirming the diagnosis of breast cancer at the time of the initial surgical consultation. However, because the cryoablation procedure will cause near complete tumor destruction (that in turn will cause immunologic effect and antitumor response), pre-cryoablation breast biopsies will be performed. At least three 18G MRI or US-guided core biopsies of the primary breast tumor will be obtained (together with core biopsies of any suspicious lymph nodes as clinically or radiographically indicated) if feasible. Two core breast specimens will be provided to the MSKCC Breast and Imaging Center (BAIC) pathology department for routine (standard of care) testing. Additional core biopsy specimens will be sent to the immune monitoring facility (IMF) for research purposes as detailed in section 12. If not all three core biopsies can be performed, this will not make the patient ineligible.

The MRI or US-guided biopsies will be performed by investigators from the Breast Radiology Service with the assistance of investigators from Interventional Radiology and Anesthesiology as needed. Image guided percutaneous cryoablation can be performed through a small nick making it a minimally invasive procedure that has been performed safely in cancer patients for many years. The cryoablation will be performed 7-10 days prior to the surgery date.

Ipilimumab and nivolumab are fully human, monoclonal anti-CTLA4 antibodies that have shown anti-tumor activity and are now US FDA approved for the treatment of patients with unresectable advanced melanoma (unresectable stage III or stage IV).

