12.0 CRITERIA FOR THERAPEUTIC RESPONSE/OUTCOME ASSESSMENT

12.1 Safety:

Safety/tolerability is the primary end point for this project.

Safety will be evaluated for all treated subjects using National Cancer Institute (NCI) Common Terminology Criteria for Adverse Events v4.0 (CTCAE). Safety assessments will be based on medical review of adverse event reports and the results of vital sign measurements, physical examinations, and clinical laboratory tests. The incidence of observed adverse events will be tabulated and reviewed for potential significance and clinical importance. The reporting period for safety data will be from the date of first on-study dose to 12 weeks after ipilimumab/nivolumab administration.

If there are no clinical signs or symptoms of toxicity, safety bloods will be done every 2-3 weeks and will include the following:

- Comprehensive metabolic panel (COMP): aspartate aminotransferase (AST), alanine aminotransferase (ALT), albumin, alkaline phosphatase (ALP), total bilirubin, calcium, creatinine, glucose, total protein, BUN, sodium, potassium, chloride, bicarbonate
- Complete blood cell count with differential and platelet count (CBC)
- Thyroid stimulating hormone (TSH)

If 5 of the 6 study patients are without an AE necessitating delay in surgery, the regimen will be considered safe/tolerable for further study.

12.2 Efficacy:

Although not a primary endpoint, exploratory correlative studies will be performed to evaluate anti-tumor and immunological response pre- and post-treatment in individuals. Comparisons with other study participants will also be conducted. Breast cancer tissue specimens, axillary lymph nodes specimens where available and peripheral blood samples will be studied. The planned exploratory correlative studies currently include:

Immune response:

The phenotypic and functional impact of the treatment will be explored by examining specimens from tumor tissue; peripheral blood (post treatment only). These tests will be done at the IMF (currently located in the Zuckerman building).

The exploratory objectives of this study are:

1. To evaluate the effect of cryoablation and ipilimumab/nivolumab administration on: lymphocyte phenotype and serum cytokines, disease related biomarkers, antibody responses to selected antigens, and humoral and cellular responses to tumor antigens and recall non-tumor antigens.

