14.0 BIOSTATISTICS

Definitive surgery confers cure for many women with early stage breast cancer and it is therefore imperative that any experimental pre-operative therapeutic innovation not undermine the timing of curative-intent surgery. Consequently, the primary endpoint for this study is safety/tolerability, as defined by the number of patients who do not develop grade 3 or 4 adverse events that necessitates a delay in surgery. Therefore, if 5 or 6 of the 6 patients are without an AE necessitating delay in surgery, the regimen will be considered safe/tolerable for further study. The probability of observing 5 or 6 patients (out of 6) who for whom therapy is safe/tolerable is 0.53 if the true safety/tolerability rate is 0.75, 0.65 if the true safety/tolerability rate is 0.80, and 0.89 if the true safety/tolerability rate is 0.90. This rule is based on the time period from start of the investigation regimen to the date of surgery, which is estimated to be approximately 15 days. Safety data up to 12 weeks following surgery will also be evaluated and reported.

Study design and analysis of the data will be performed with the assistance of [name], Division of Epidemiology and Biostatistics.

This is a pilot study using innovative methods and if cryoablation and single-dose ipilimumab/nivolumab is deemed safe, will result in the design of a larger trial. As such, there is no formal statistical analysis or sample size calculation for this study. All analysis will be descriptive in nature and the sample size is dictated by drug availability and budget constraints.

We have several exploratory secondary analyses. As noted above, all analyses will be evaluated descriptively and graphically. Serum and tumor biomarker levels (including lymphocytes and DC's) and serum cytokines will be plotted over the study timepoints. The ratio of specific intra-tumoral and serum t cell populations (i.e. CD4+FOXP3+ T-regulatory cells (Tregs) to CD8+Effector cells) will also be plotted over study timepoints. Other endpoints that will be summarized descriptively include ALC, and absolute T cell count.

Estimated accrual will be approximately 2-3 patients per month, making targeted completion of accrual within approximately 2 to 3 months of the study initiation.

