20.0 APPENDICES

Appendix 1: Study Timetable

Visit	Visit #1: 1 st Surgical Appointment	Visits #2 and #3: MD and IR evaluation appointments (to be coordinated whenever feasible)	Visit #4: Ipilimumab/ nivolumab date	Visit #5: Core biopsy/ cryoablation date	Visit #6: Safety assessment (1 day prior or day of surgery)	Visit #7: Surgery date	Visit #8 +: Safety assessment 2- 3 weeks post- surgery and every 2-3 weeks thereafter until 12 weeks post ipi/nivo
Potential candidates identified	X						
Surgery date set	X						
Presurgical testing date set	X						
Cryoablation amenability determined by Radiology		X					
Consent signed		X					
Ipilimumab/nivolumab date set/appt with MD		X					
Ipi/nivo infusion			X				
Core biopsy x≥3				X			
Research Blood samples*			X	X	X		X ¹
Safety blood work (CBC, Comp, TSH)							X
Pathology review	X						
History & Physical exam	X	X	X		X		X

* Baseline study bloods (CBC, COMP, TSH, Free T4, T3, ACTH, FSH, LH, Prolactin, Testosterone levels, HIV, Hep B, Hep C), EKG, vital signs, and research bloods may be tested with routine pre-surgical testing or on the day of ipilimumab/nivolumab administration. HIV, Hep B, and Hep C can be drawn within 60 days of study registration.

**Memorial Sloan Kettering Cancer Center
IRB Protocol #: 16-495 A(5)
Approved: 3-MAY-2017**

§this appointment will be coordinated with off-study surgery follow-up appt if feasible, visits 9 and 10 (if applicable) will be done every 2-3 for safety assessments up to 12 weeks after ipilimumab/nivolumab administration

1. Post surgery research bloods will be collected 30 days (+/-10 days) after surgery completion.

Appendix 2: General Recommendation for Management of Suspected Immune Related Adverse Events (irAE)

A general principle is that differential diagnoses should be diligently evaluated according to standard medical practice. Non-inflammatory etiologies should be considered and appropriately treated.

[figure not shown]
Corticosteroids are a primary therapy for immuno-oncology drug-related adverse events. The oral equivalent of the recommended IV doses may be considered for ambulatory patients with low-grade toxicity. The lower bioavailability of oral corticosteroids should be taken into account when switching to the equivalent dose of oral corticosteroids.

Consultation with a medical or surgical specialist, especially prior to an invasive diagnostic or therapeutic procedure, is recommended.

GI ADVERSE EVENT MANAGEMENT ALGORITHM

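### Safety visits start from surgery and women without the planned surgery are removed, so scheduled follow-up of dosed women can fall short of the 12 weeks in Section 12.1

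*Combined protocol and SAP*

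**What the plan says.** Section 13.0 has two removal rules that matter here. One is discretionary: "Subjects may be removed from the study at any time due to severe unacceptable side effects, life-threatening events". The other is mandatory: "For all participants, failure to have the planned surgery at MSKCC will result in removal from the study". Neither separates women who have received study drug from those who have not, and Section 13.0 does not say what safety follow-up continues after removal.

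Appendix 1 heads its last column "Visit #8 +: Safety assessment 2- 3 weeks post- surgery and every 2-3 weeks thereafter until 12 weeks post ipi/nivo". The schema in Section 1.0 has the same surgery-based start and runs to at least 12 weeks after dose. Appendix 1 marks post-baseline safety bloods (blood count, metabolic panel, TSH) only in that column. The safety assessment before it, Visit 6, is set for the day before or the day of surgery.

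Section 12.1 says: "Safety will be evaluated for all treated subjects using National Cancer Institute (NCI) Common Terminology Criteria for Adverse Events v4.0 (CTCAE"). Its reporting period runs from first dose to 12 weeks after dose. It also mentions bloods every 2-3 weeks, but gives no start date and words this for women without clinical signs or symptoms of toxicity.

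Under Section 4.2, what counts against the regimen is "side effects from intervention resulting in a delay of their planned surgery date, this will be a failure of the primary endpoint". Section 14.0 defines the endpoint as "the number of patients who do not develop grade 3 or 4 adverse events that necessitates a delay in surgery" and applies the rule from the start of the regimen to surgery.

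**The concern.** The event that fails the primary endpoint, a delayed operation, is also the event that moves the visit schedule. Because the start of the series follows surgery and its end is fixed to the dose, a delay both postpones the first visit and reduces the number of visits. A woman who does not have the planned operation at the centre fares worse on paper: she must be removed, and Visits 6 and 8+ have no date.

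At stake is the 12-week adverse event summary. If scheduled observation shrinks because of early toxicity, the women who had that toxicity have fewer chances to show later events, and the summary tends to look cleaner than it should. With six women, one incomplete record matters. Some of these events need a blood test to be found: Section 3.0 notes that liver test elevations can occur without symptoms.

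**Working it through.** **1. The plan's own figures.** For 5 or 6 successes out of 6, P = 6p⁵(1 − p) + p⁶.

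- p = 0.75: 0.5339 (plan: 0.53)
- p = 0.80: 0.6554 (plan: 0.65)
- p = 0.90: 0.8857 (plan: 0.89)

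These reproduce to within rounding. Nothing below changes them.

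**2. Timing inputs, with dose on day 0.**

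- Surgery on day 8-15 (Section 4.2; equally 7 + 1 to 10 + 5 from Section 9.0).
- First Visit 8+ 14-21 days after surgery, then every 14-21 days (Appendix 1).
- End of window on day 84 (Section 12.1, Appendix 1).
- Delay d: the protocol gives no length, so a range is assumed.

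**3. Formulas.** The first visit lies between 8 + d + 14 = 22 + d and 15 + d + 21 = 36 + d. If the first visit is on or before day 84, the number of visits by day 84 is floor((84 − first)/interval) + 1. The maximum uses the earliest first visit and 14-day spacing; the minimum uses the latest first visit and 21-day spacing. With no delay:

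- maximum: floor((84 − 22)/14) + 1 = 5
- minimum: floor((84 − 36)/21) + 1 = 3

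| Assumed delay | Surgery, day | First Visit 8+, day | Visits by day 84 |
|---|---|---|---|
| none | 8-15 | 22-36 | 3-5 |
| 2 weeks | 22-29 | 36-50 | 2-4 |
| 4 weeks | 36-43 | 50-64 | 1-3 |
| 6 weeks | 50-57 | 64-78 | 1-2 |
| 7 weeks | 57-64 | 71-85 | 0-1 |
| 9 weeks | 71-78 | 85-99 | 0 |

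The schema's wording of at least 12 weeks would allow a visit after day 84, but that visit falls outside the Section 12.1 reporting period.

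**4. No operation at the centre.** Section 13.0 removes the woman, and the surgery-based visits have no date. If removal takes effect on the planned surgery date, the part of the window without scheduled visits is 84 − 15 = 69 to 84 − 8 = 76 days, or 82-90% of 84. This describes scheduled visits for a removed woman only.

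**5. What continues regardless.** Section 17.2 requires reporting of serious events for 30 days after the last intervention. With cryoablation 1-5 days after dose, that is day 31-35. Events after that must be reported if at least possibly related. Section 17.2.1 follows serious events to resolution or stabilization, and requires follow-up of nonserious events still present when participation ends. None of these provisions schedules a visit or a blood test to find a new event.

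**6. A second mismatch.** Section 14.0 says safety data to 12 weeks after surgery will be reported. With no delay that is day 8 + 84 = 92 to 15 + 84 = 99, against day 84 in Section 12.1. The Appendix 1 visits stop at 12 weeks after dose, so the extra days have no scheduled assessment.

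**The case against.** The strongest reply is that Section 12.1 already covers these women: it names all treated subjects, fixes 12 weeks from dose and mentions bloods every 2-3 weeks without reference to surgery. Section 17.2 adds reporting and follow-up that do not depend on staying in the study. This stands in part. Safety data collection does not stop, and the plan's intent is clear. But the Section 12.1 bloods have no start date and are worded for women without signs of toxicity, while the timetable that staff would follow starts from surgery. Women with toxicity are referred to Appendix 2, whose algorithm figures are not legible in the available text, so any monitoring they specify cannot be credited or ruled out.

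Three stronger readings are tempting and are not supported.

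- A reader might infer that women who fail the endpoint are removed. The failure is a delay. A late operation at the centre is not clearly a failure to have the planned surgery, and removal for side effects is only permitted.
- A reader might combine the 82-90% figure with the expected number of failures at the Section 14.0 rates, 6 × (1 − p) = 1.5, 1.2 and 0.6. Those are delay failures; the documents give no number for women removed. Nor does 82-90% describe all safety data, since serious-event reporting continues.
- A reader might infer that after a single dose and ablation, removal can only mean the end of safety follow-up. It can also end research sampling or, before day 1-5, a pending ablation. Section 13.0 is silent on safety follow-up; it does not forbid it.

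Nor do the onset figures in Section 3.0 (median about 61 days; endocrine events at weeks 6-12) show that delayed women go unobserved when toxicity peaks. The 61-day median comes from repeated dosing in melanoma. After a 4-week delay the visits begin on day 50-64, inside that period.

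**Conclusion.** The point holds as a conflict between sections. Followed as written, Section 13.0 and Appendix 1 do not deliver the scheduled follow-up needed to support the Section 12.1 evaluation of all treated subjects. For a delayed operation, visits within 84 days fall from 3-5 to 2-4, 1-3 or 1-2 under assumed delays of 2, 4 or 6 weeks; none may remain from 7 weeks, and none do from 9. For a woman without the planned operation at the centre, no visit is dated.

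The loss is of scheduled visits and bloods that would detect new events, not of all safety information. The sizes rest on assumed delays and on a literal reading of Appendix 1. The go/no-go rule, "if 5 or 6 of the 6 patients are without an AE necessitating delay in surgery", is judged at surgery, so a delay failure has already been seen and the decision does not change. The consequence is confined to the descriptive 12-week summary, where missing observations would be related to toxicity. It is worth correcting because the correction is cheap.

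**What to change.** Reconcile Section 13.0 and Appendix 1 with Section 12.1.

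- In Section 13.0, state that removal of a woman who has received study drug ends further protocol interventions and research sampling, but not safety data collection through the Section 12.1 window (12 weeks after dose), unless she withdraws consent for follow-up.
- In Appendix 1 and the schema, put the safety assessments on the same dose-based clock as the Section 12.1 window, so that a delayed or cancelled operation neither moves nor removes them. They can still be combined with post-operative appointments when dates coincide.
- State one reporting window for Sections 12.1 and 14.0.

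The clinical content of the assessments and the management of toxicity are for the investigators and are not touched by this change.

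The cost is amendment wording, plus a few extra visits or outside laboratory results for perhaps one or two women. Obtaining data from a woman operated on elsewhere will take some effort. The sample size, the decision rule and its stated probabilities stay as they are.

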14.0 BIOSTATISTICS

Definitive surgery confers cure for many women with early stage breast cancer and it is therefore imperative that any experimental pre-operative therapeutic innovation not undermine the timing of curative-intent surgery. Consequently, the primary endpoint for this study is safety/tolerability, as defined by the number of patients who do not develop grade 3 or 4 adverse events that necessitates a delay in surgery. Therefore, if 5 or 6 of the 6 patients are without an AE necessitating delay in surgery, the regimen will be considered safe/tolerable for further study. The probability of observing 5 or 6 patients (out of 6) who for whom therapy is safe/tolerable is 0.53 if the true safety/tolerability rate is 0.75, 0.65 if the true safety/tolerability rate is 0.80, and 0.89 if the true safety/tolerability rate is 0.90. This rule is based on the time period from start of the investigation regimen to the date of surgery, which is estimated to be approximately 15 days. Safety data up to 12 weeks following surgery will also be evaluated and reported.

Study design and analysis of the data will be performed with the assistance of [name], Division of Epidemiology and Biostatistics.

This is a pilot study using innovative methods and if cryoablation and single-dose ipilimumab/nivolumab is deemed safe, will result in the design of a larger trial. As such, there is no formal statistical analysis or sample size calculation for this study. All analysis will be descriptive in nature and the sample size is dictated by drug availability and budget constraints.

We have several exploratory secondary analyses. As noted above, all analyses will be evaluated descriptively and graphically. Serum and tumor biomarker levels (including lymphocytes and DC's) and serum cytokines will be plotted over the study timepoints. The ratio of specific intra-tumoral and serum t cell populations (i.e. CD4+FOXP3+ T-regulatory cells (Tregs) to CD8+Effector cells) will also be plotted over study timepoints. Other endpoints that will be summarized descriptively include ALC, and absolute T cell count.

Estimated accrual will be approximately 2-3 patients per month, making targeted completion of accrual within approximately 2 to 3 months of the study initiation.

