The purpose of the study is to determine the safety of pre-operative ipilimumab, nivolumab and cryoablation in patients with biopsy proven resectable breast cancer. If at least 5 of the 6 patients are without an adverse event (AE) necessitating delay in surgery, the regimen will be considered safe/tolerable for further study. Secondary aims of this study are to explore and characterize pre- and post-intervention peripheral and tumor responses to ipilimumab, nivolumab and cryoablation.

Med Onc and Cryoablation Evaluation Appointments

At First Visit For Potential Study Candidates in Surgery Clinic

- Non-study surgery date is scheduled
- Non-study pre-surgical testing date is scheduled
- Informed consent is provided
- Initial Med Onc and Cryoablation Evaluation appointments, if feasible, are scheduled to occur as soon as possible

Med Onc and Cryoablation Evaluation Appointments

- Potential study candidates evaluated for eligibility
- If eligible then:
 - Informed consent signed
 - Core biopsy (+ cryoablation) date set for 7-10 days before surgery
 - Ipilimumab + nivolumab date set for 1-5 days before core biopsy/cryoablation date
 - Post-op follow-up appointment with Med Onc set

Eligibility/Baseline study bloods (coordinated with routine Pre-Surgical Testing whenever feasible) *

Ipilimumab + Nivolumab Date* (1-5 days before biopsy/cryoablation)

Appt. with Med Onc

Ipilimumab + nivolumab administered

Core Biopsy + Cryo Date* (7-10 days before surgery)

Core biopsy x ≥ 3

Cryoablation

Surgery Date*

Safety assessment 2-3 weeks post-surgery (coordinated with off-study surgery follow-up appt if feasible) and then every 2-3 weeks thereafter until at least 12 weeks post ipilimumab and nivolumab date. #

All Arms: Research bloods 30 (+/-10) days after surgery.*

* Indicates time points for obtaining Research blood samples. Baseline study bloods may be drawn with routine pre-surgical testing or on the day of ipilimumab injection (if applicable), prior to drug administration.

Indicates time points for obtaining Safety blood Samples

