- **Immune-related Adverse Events (irAE):** Many of the adverse events considered related to ipilimumab are immune in nature and presumably a consequence of the intrinsic biological activity of ipilimumab. In prior ipilimumab clinical studies, an irAE was defined as any adverse event associated with drug exposure and consistent with an immune-mediated event. Disease progression, infections and other etiologic causes were ruled out or deemed unlikely as contributing to the event. Supportive data, such as autoimmune serology tests or biopsies, were considered to be helpful but not necessary to categorize an event as an irAE. Events of unclear etiology which were plausibly immune mediated were conservatively categorized as irAEs even if serologic or histopathology data were absent. These irAEs likely reflect a loss of tolerance to some self-antigens or an unchecked immune response to gut or skin flora. Some breakthrough of immunity may be inseparably linked to the clinical antitumor activity of ipilimumab. Immune-related adverse events predominately involve the GI tract, endocrine glands, liver or skin. Experience with ipilimumab indicates that irAEs are typically low grade and self-limited, with few exceptions; irAEs were clinically manageable and reversible with supportive care or corticosteroids (see treatment algorithm Appendix 2-6). Notably, IrAE typically occur after multiple doses of ipilimumab. In this study a single 1mg/kg dose of ipilimumab is being administered, which make irAE unlikely. This is supported by a recently reported study wherein presurgical ipilimumab administration in patients with bladder cancer was tolerable and safe.¹²
- **Gastrointestinal irAEs:** The most common grade 3 or greater irAE involved the lower GI tract and clinically manifested as diarrhea or hematochezia. Diarrhea resulting from treatment with ipilimumab ranged from mild to severe and was life-threatening in some cases. Some cases of diarrhea began as mild and became very severe (Beck 2006). Serious GI irAEs mostly involved diarrhea or colitis (e.g. hemorrhagic colitis that was unresponsive to medical management and necessitated colectomy, bowel wall perforations associated with and without ipilimumab-induced colitis). Diarrhea/colitis is one of the most serious AEs and must be evaluated in a timely fashion (see diarrhea management algorithm in Appendix 4). All patients with diarrhea will be seen by physician and evaluated with a CT Scan/colonoscopy if necessary.

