9.0 TREATMENT/INTERVENTION PLAN

Patients will undergo breast biopsy with cryoablation 7-10 days prior to the planned surgery, and ipilimumab with nivolumab administration 1-5 days before cryoablation. All patients will undergo surgery at the pre-determined day defined at the initial surgical consultation as detailed in section 4.1.

9.1 Ipilimumab and Nivolumab:

Women will receive ipilimumab and nivolumab 1-5 days prior to US or MRI-guided core biopsy and cryoablation date. Intravenous ipilimumab will be administered as a single 1 mg/kg dose to be infused intravenously over 90 minutes in the chemotherapy suite of the BAIC. Intravenous nivolumab will be administered as a single 3 mg/kg dose to be infused intravenously over 60 minutes in the chemotherapy suite of the BAIC.

In a study reported by [name] of various doses of ipilimumab and nivolumab in combination in metastatic melanoma, there was a 98% AE rate, a 93% treatment related AE rate, a 72% grade 3/4 AE rate, a 53% treatment related grade 3/4 AE rate and a 49% serious AE rate.⁶¹ Toxicity with both drugs administered at 3mg/kg was considered unacceptable, and nivolumab at 1mg/kg with ipilimumab at 3mg/kg was considered the maximum dose with an “acceptable” level of AEs - a threshold which is unlikely to be “acceptable” in the curative setting. Thus, combination therapy with ipilimumab administered at 1mg/kg and nivolumab administered at 3mg/kg was recommended and will be the dose we will administer for this study.

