17.2.1 Additional Information on Serious Adverse Event (SAE) Reporting

Collection of Safety Information

An Adverse Event (AE) is defined as any new untoward medical occurrence or worsening of a pre-existing medical condition in a patient or clinical investigation subject administered an investigational (medicinal) product and that does not necessarily have a causal relationship with this treatment. An AE can therefore be any unfavorable and unintended sign (including an abnormal laboratory finding, for example), symptom, or disease temporally associated with the use of investigational product, whether or not considered related to the investigational product.

Although overdose and cancer are not always serious by regulatory definition, these events should be reported on an SAE form and sent to BMS in an expedited manner. An overdose is defined as the accidental or intentional ingestion or infusion of any dose of a product that is considered both excessive and medically important.

Note that all pregnancies, regardless of outcome, must be reported to the sponsor on a Pregnancy Surveillance Form, not an SAE form. All pregnancies must be reported and followed to outcome, including pregnancies that occur in the female partner of a male study subject. See Section 8.4 for instructions on reporting pregnancies.

Nonserious Adverse Events

All adverse events that are not classified as serious.

Assignment of Adverse Event Intensity and Relationship to Investigational Product

All adverse events, including those that are serious, will be graded according to the National Cancer Institute Common Toxicity Criteria for Adverse Events (NCI CTCAE), Version 4.0.

The following categories and definitions of causal relationship to investigational product as determined by a physician should be used for adverse events:

- Definite: The AE is clearly related to the intervention.
- Probable: The AE is likely related to the intervention.
- Possible: The AE may be related to the intervention.
- Unlikely: The AE is doubtfully related to the intervention.
- Unrelated: The AE is clearly NOT related to the intervention.

Collection and Reporting

Adverse events can be spontaneously reported or elicited during open-ended questioning, examination, or evaluation of a subject. (In order to prevent reporting bias, subjects should not be questioned regarding the specific occurrence of one or more AEs.)

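### The primary endpoint is limited to grade 3/4 adverse events that delay surgery, but the go/no-go rule and Section 4.2 count delays of any grade, so the trial's verdict can depend on which sentence is applied

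*Combined protocol and SAP*

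**What the plan says.** Section 14.0 gives the primary endpoint as "the number of patients who do not develop grade 3 or 4 adverse events that necessitates a delay in surgery". The sentence that follows sets the decision rule without a grade: the regimen is declared safe "if 5 or 6 of the 6 patients are without an AE necessitating delay in surgery". The rule appears twice more, again without a grade: "If at least 5 of the 6 patients are without an adverse event (AE) necessitating delay in surgery" in Section 1.0 and "If 5 of the 6 study patients are without an AE necessitating delay in surgery" in Section 12.1.

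Section 4.2 speaks of the endpoint itself, patient by patient: if a patient has "side effects from intervention resulting in a delay of their planned surgery date, this will be a failure of the primary endpoint". It too has no grade limit. The date against which delay is judged is fixed in Section 9.0: "All patients will undergo surgery at the pre-determined day defined at the initial surgical consultation".

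The sections also differ on attribution. Section 4.2 counts side effects of the intervention. Sections 1.0, 12.1 and the rule in 14.0 count an AE, which Section 17.2.1 defines as an occurrence "that does not necessarily have a causal relationship with this treatment".

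**The concern.** A grade 2 event caused by the intervention that postpones surgery is a success under the endpoint sentence of Section 14.0 and a failure under Section 4.2. Both sentences describe the same primary endpoint. Section 14.0 justifies the endpoint by the need to keep curative surgery on time, and a postponement harms timing whatever the grade of its cause. Read literally, the endpoint sentence also leaves out grade 5.

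The 5-of-6 rule produces the trial's only go/no-go conclusion, and Section 14.0 says that a favourable result leads to a larger trial. If the definition is not settled beforehand, the conclusion can turn on a reading chosen after the events are known.

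**Working it through.** **Inputs.** There are six patients in one arm (Section 1.0), and the regimen passes with at least 5 successes, that is, at most 1 failure (Section 14.0). The documents give neither the any-grade delay rate *d* nor the share *g* of delays caused by grade 1-2 events. Both are assumptions here.

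**The plan's own figures.** With true success rate *p*, P(pass) = p^6 + 6p^5(1 − p).

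- p = 0.75: 0.1780 + 0.3560 = 0.534 (plan: 0.53)
- p = 0.80: 0.2621 + 0.3932 = 0.655 (plan: 0.65)
- p = 0.90: 0.5314 + 0.3543 = 0.886 (plan: 0.89)

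These reproduce. They are functions of a generic rate and are not wrong under either definition. What is left open is which rate *p* refers to.

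**When the readings conflict.** Let D be the number of patients delayed by an AE of any grade, and G the number of those delayed by a grade 3 or 4 AE, with 0 ≤ G ≤ D ≤ 6. The any-grade reading passes if D ≤ 1 and the grade-limited reading passes if G ≤ 1. Of the 28 possible (D, G) pairs, 10 give opposite verdicts: D = 2 to 6 with G = 0 or 1. In all 10 the grade-limited reading says safe and the any-grade reading says not safe. For example, one grade 3 delay plus one grade 2 delay is 5/6 (safe) under the endpoint sentence and 4/6 (not safe) under the rule.

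**How often.** Write F(q) = (1 − q)^6 + 6q(1 − q)^5 for the chance of at most one failure at failure rate q. The any-grade reading passes with probability F(d), the grade-limited one with F(d(1 − g)). Passing the first implies passing the second, so

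P(opposite verdicts) = F(d(1 − g)) − F(d).

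For d = 0.20 and g = 0.5 this is F(0.10) − F(0.20) = 0.886 − 0.655 = 0.230 (from unrounded values).

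| d | F(d) | P(opposite), g = 0 | g = 0.25 | g = 0.5 |
|---|---|---|---|---|
| 0.05 | 0.967 | 0 | 0.014 | 0.024 |
| 0.10 | 0.886 | 0 | 0.045 | 0.081 |
| 0.20 | 0.655 | 0 | 0.121 | 0.230 |
| 0.25 | 0.534 | 0 | 0.152 | 0.300 |

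The rates 0.10, 0.20 and 0.25 correspond to the plan's 0.90, 0.80 and 0.75 scenarios if those are read as any-grade rates. Under the endpoint sentence the scenarios would instead fix d(1 − g).

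The grid is not a bound. With three quarters of delays at grade 1-2 (g = 0.75), the chance is 0.312 at d = 0.20 and 0.417 at d = 0.25.

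**Given that two or more patients are delayed.** Dividing by 1 − F(d), which is 0.033, 0.114, 0.345 and 0.466 for the four rates, the readings conflict with probability 0.42, 0.40, 0.35 and 0.33 for g = 0.25, and 0.73, 0.71, 0.67 and 0.64 for g = 0.5.

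**The case against.** The grade limit appears once, against four statements without it. The rule follows the endpoint sentence with a linking word of consequence, so one could call the limit a stray qualifier that the rule overrides. One could equally read AE in the rule as shorthand for the grade 3 or 4 event just defined. The text does lean towards any grade. But the linking word supports either reading, Sections 1.0, 4.2 and 12.1 stand without the limit, and no sentence settles the matter.

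Conflict may also be rare. Section 3.0 argues "In this study a single 1mg/kg dose of ipilimumab is being administered, which make irAE unlikely", and reports a median onset of about 61 days (range 4 to 114) in melanoma patients given repeated doses of the combination, against a window of about 15 days here. That points to the low end of the table and is a fair limit on the size. It does not remove the contradiction, which matters only once two or more delays have occurred, and then it matters often.

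Finally, the analysis is descriptive, and Section 12.1 has all adverse events tabulated, so a low-grade delay would not be hidden. That is true, but the plan still attaches a declared verdict to the count, and the verdict would differ.

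**Conclusion.** The concern holds. The endpoint sentence in Section 14.0 contradicts the rule beside it and Sections 1.0, 4.2 and 12.1 on grade, and the documents do not say which governs. The conflict arises exactly when at least two patients are delayed and at most one has a grade 3 or 4 cause, and it always makes the grade-limited reading the lenient one. These results follow from the wording and need no assumption.

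The probabilities do need assumptions: independent patients, a common delay rate and an assumed share of grade 1-2 causes. With that share between 0 and one half and delay rates of 5% to 25%, the chance of opposite verdicts runs from 0 to 0.30. It is higher if low-grade causes predominate. Attribution is a second, separate ambiguity. It is not quantified, because the documents give no rate of unrelated delays.

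**What to change.** In Section 14.0, delete the grade limit from the endpoint sentence, so that the endpoint counts patients with no adverse event of any grade that postpones surgery past the pre-determined date in Section 9.0. On grade, this brings the sentence into line with its own rule and with Sections 1.0, 4.2 and 12.1. Report delays caused by grade 3 or higher events as a descriptive breakdown.

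Separately, add one sentence that reconciles Section 4.2 with Sections 1.0, 12.1 and 14.0 on whether events unrelated to the intervention count. That choice is the sponsor's.

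The cost is one wording edit and one added sentence, with no new data or visits. The pass probability falls, relative to the grade-limited reading, by the amounts in the table (0 to 0.30 on those assumptions, more if low-grade causes predominate). Both edits should be made before enrolment. The documents do not state enrolment status, and if patients have already been treated, the change should be dated and declared as a clarification of the primary endpoint. The removal and replacement rule in Section 13.0 is a separate matter that this edit does not settle.
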